#### Graft Failure

Islet transplant recipients who have graft failure (absence of insulin production, with (c-peptide <0.1 nmol/L (<0.3 ng/mL) are eligible to undergo a second islet transplant if they meet the eligibility criteria described below:

- Prior to day 75, repeat transplantation within the CIT protocol must be approved by the CIT Steering Committee, based upon review of clinical information provided by the transplanting site to the DCC.
- After day 75, repeat transplantation must be approved by the Nordic Network Steering Committee, based on clinical information provided by the site. The decision of the Nordic Network Steering Committee will be provided to the sponsor.

Clinical information provided must include:

1) Results of graft failure assessments

- a) random c-peptide <0.1 nmol/L (<0.3 ng/mL)
- b) c-peptide <0.1 nmol/L (<0.3ng/mL) at baseline, and at 60 and 90 minutes after MMTT.
- 2) Post transplant clinical data
- 3) Potency testing from the first transplant product
- 4) Additional assessments as requested from the CIT Steering Committee.

Eligibility criteria include:

- 1. Subject has been compliant with study monitoring and prescribed immunosuppressive therapy;
- 2. No evidence of a serious and life-threatening infection, adverse event, or other condition that precludes attempting an intraportal injection or continuation of the post-transplant treatment regimen;
- 3. No evidence of post-transplant lymphoproliferative disorder (PTLD);
- 4. No evidence of progressive renal dysfunction, defined as creatinine rising above 2.0 mg/dL (177  $\mu$ mol/L) with calcineurin inhibitor trough levels within maintenance levels;
- 5. No evidence of hypersensitization, allergic responses, or other potentially serious drug reactions to medications required by the protocol.
- 6. Less than 8 months has passed after the first transplantation.
- 7. Absence of any medical condition that, in the opinion of the investigator, will interfere with a safe and successful second islet transplant.

If after the second islet infusion both basal and stimulated C-peptide levels remain <0.1nmol/L (<0.3 ng/mL), these recipients will be considered treatment failures with no islet graft function, and immunosuppression will be withdrawn.

Islet transplant recipients who do not meet criteria for full islet graft function **after the second islet infusion**, but before 8 months from the first infusion will be considered for a **third islet infusion**.

The option of a third islet infusion under this protocol will be considered if the subject is  $\geq$ 28 days (+/-3 days) following the second islet infusion, and if all of the following conditions are met:

- 1. The subject remains without full islet graft function;
- 2. There is evidence of partial graft function (C-peptide > 0.1nmol/L (>0.3ng/mL);
- 3. No evidence of post-transplant lymphoproliferative disorder (PTLD);
- 4. The CIT Principal Investigator and Site Principal Investigators have determined that there were no relevant protocol deviations at the site;
- 5. The subject has been compliant with study monitoring and prescribed immunosuppressive therapy;
- 6. No evidence of a serious and life-threatening infection, adverse event, or other condition that precludes attempting an intraportal injection or continuation of the post-transplant treatment regimen;
- No evidence of progressive renal dysfunction, with blood creatinine rising above 2.0 mg/dL (177 μmol/L);
- 8. No evidence of hypersensitization, allergic responses, or other potentially serious drug reactions to medications required by the protocol;
- 9. No evidence of abnormal liver ultrasound and LFTs within 1.5 times the upper limit of the normal range prior to the third transplant.
- 10. Less than 8 months has passed after the first islet transplantation.

Participants who have completed 8 months follow up post first infusion will no longer be eligible for additional islet infusions funded under this protocol.

## 7.5 Follow Up Schedule and Procedures

Subjects will undergo clinical evaluation by the investigator and/or their designee at screening, baseline, transplantation, days 1, 3, 7, 14, 21, 28, 75, and months 6 and 12 (Appendix 1). Clinical safety will be monitored through routine physical examinations and appropriate laboratory assessments. During the study, subjects will have repeated clinical and laboratory evaluations, as specified in the Schedule of Events. The timing of all follow-up assessments will reset at the time of subsequent transplants (i.e., the day of the second transplant becomes day 0, and all assessments are conducted in relation to this day).

Evaluations should be made for sirolimus, cyclosporine and tacrolimus levels, as applicable. Immunosuppression levels will be monitored from time of transplantation until the end of the study.

# 7.6 Subject Self Monitoring Plasma Glucose

Investigators should instruct subjects to measure and keep notes of pre and postprandial plasma glucose and requirement of insulin, from the time of enrollment until completion of the study. Data should be recorded before breakfast, at lunch and dinner, and then two hours after each of these meals, and once in the evening. If the subject becomes free of insulin it is sufficient to record the data of blood/plasma glucose two days per week up until 12 months post transplant. All subjects will use the Ultra One Touch® glucose monitoring units, provided by the study center. Subject diaries should be collected as specified in the Schedule of Events, and kept as source documentation.

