# **Study Definitions Page**

Control Arm- State of the Art	The study treatment group randomized to receive protocol specified immunosuppression without LMW-DS, including anticoagulative treatment with Heparin with the islet infusion.
Experimental Arm- Low Molecular Weight Sulfated Dextran	The study treatment group randomized to receive protocol specified immunosuppression with Low Molecular Weight Sulfated Dextran (LMW-DS), and excluding Heparin treatment.
Full Islet Graft Function	
 
Islet transplant recipients are considered to have full islet graft function if all of the following criteria are met: 
 
Titrated off insulin therapy for at least 1 week (7 consecutive days) with the last day within the day 75 and day 365 windows;
 
One HbA1c level, one fasting serum glucose level, and Mixed Meal Tolerance Test are documented within the visit window (e.g. 70-80 days at Day 75) and 7 consecutive days of blood sugar and insulin readings are documented within +/- 7 days of the visit window (e.g. 63-87 days at Day 75);
 
HbA1c <7.0% or a ≥2.5% decreased from baseline;
 
Fasting capillary glucose level should not exceed 140 mg/dL (7.8 mmol/L) more than three times in the 7 consecutive days (fasting is defined as 1st blood sugar reading of the day not noted as post-prandial or bedtime). Post-prandial capillary glucose level ≤ 126 mg/dL (≤7.0 mmol/L) at 90 minutes during the MMTT;
 
Fasting serum glucose level ≤ 126 mg/dL (≤7.0 mmol/L) from central lab results; if the fasting serum glucose level is > 126 mg/dL (>7.0 mmol/L), it must be confirmed in an additional one out of two measurements;
 
At least one MMTT fasting or stimulated c-peptide ≥0.5 ng/ml.
 
 
 

Graft Failure	Islet allograft failure will be defined as absence of insulin production by transplanted islets, as evidenced by absence of c-peptide <0.1nmol/L (<0.3 ng/mL). This will be determined by: (1) c-peptide <0.1nmol/L (<0.3 ng/mL) on random testing, followed by (2) c-peptide <0.1nmol/L (<0.3 ng/mL) at baseline, and at 60 and 90 minutes after MMTT. C-peptide levels obtained in the course of the MMTT levels will be run at the core laboratory in Seattle, WA. Subjects with graft failure do not need to complete the day 75 metabolic assessment.

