### 4.1.3.1 FULL ISLET GRAFT FUNCTION DEFINITION:

Islet transplant recipients are considered to have full islet graft function if all of the following criteria are met:

- Titrated off insulin therapy for at least 1 week (7 consecutive days) with the last day within the day 75 and day 365 windows;
- HbA1c <7.0% or a 2.5%% decreased from baseline at the end of the 7 day period when titrated off insulin;
- Fasting capillary glucose level should not exceed 140 mg/dL (7.8 mmol/L) more than three times in the past week (based on measuring capillary glucose levels a minimum of 7 times in a seven day period);
- 2-hour post-prandial capillary glucose should not exceed 180 mg/dl (10.0 mmol/L) more than three times in the past week (based on measuring capillary glucose levels a minimum of 21 times in a seven day period);
- Fasting serum glucose level ≤ 126 mg/dL (≤7.0 mmol/L) from central lab results; if the fasting serum glucose level is > 126 mg/dL (>7.0 mmol/L), it must be confirmed in an additional one out of two measurements;
- Evidence of endogenous insulin production defined as fasting or stimulated C-peptide levels ≥ 0.5 ng/mL (≥0.16 nmol/L) at the end of the 7 day period when titrated off insulin.

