## 9. MECHANISTIC ASSAYS

## 9.1 Metabolic Testing

All subjects will use a study provided One Touch Ultra glucometer or an approved glucometer and/or CGMS unit identified in the MOP for measuring capillary glucose levels. Investigators should instruct subjects to measure and keep notes of pre and postprandial plasma glucose and requirement of insulin. Data should be recorded before breakfast, at lunch and dinner, and then two hours after each of these meals, and once in the evening. If the subject becomes free of insulin it is sufficient to record the data of blood/plasma glucose two days per week up until 12 months post transplant. Subject diaries should be collected as specified in Appendix I, Schedule of Events, and kept as source documentation. Glucometers will be collected and measurements downloaded as specified in the Schedule of Events.

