#### 9.1.1.3 GLYCEMIC LABILITY

Glycemic lability will be assessed by both the mean amplitude of glycemic excursions (MAGE) and the lability index (LI).

The MAGE requires 14 – 16 capillary blood glucose (BG) measurements over two consecutive days taken before and 2-hours after breakfast, lunch, and dinner, and at bedtime with an optional measurement at 3 AM. A glycemic excursion is calculated as the absolute difference in peak and subsequent nadir (or vice versa) glucose values, with the direction (peak to nadir versus nadir to peak) determined by the first quantifiable excursion in the two day period. All excursions > 1 S.D. of the 7 – 8 glucose readings for the day in which they occurred qualify for the analysis, where they are summed and divided by the number of qualified excursions to give the MAGE in mmol/L (or mg/dL) glucose. A MAGE > 11.1 mmol/L (200 mg/dl) is indicative of marked glycemic lability.

The LI requires 4 or more daily capillary BG measurements over a 4 week period and is calculated as the sum of all the squared differences in consecutive glucose readings divided by the hours apart the readings were determined (range 1 to 12 hours) in  $(mmol/L^2/hr \cdot wk^{-1})$ . A LI greater than or equal to the 90th percentile (433 mmol/L/hr ·wk) of values derived from an unselected group of type 1 diabetes (T1D) patients is evidence for severe glycemic lability.

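### The two-day recording allowance for insulin-free subjects conflicts with the diary data that full islet graft function and the lability index require

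*Protocol*

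**What the plan says.** **The allowance.** Section 7.6 sets a seven-point recording day: "Data should be recorded before breakfast, at lunch and dinner, and then two hours after each of these meals, and once in the evening". It then relaxes this: "If the subject becomes free of insulin it is sufficient to record the data of blood/plasma glucose two days per week", up to 12 months after transplant. Section 9.1 repeats the allowance. Neither section excludes the weeks before an endpoint visit.

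**Full islet graft function** (secondary endpoint at Day 75 and Day 365). The Study Definitions Page requires the subject to be off insulin: "Titrated off insulin therapy for at least 1 week (7 consecutive days) with the last day within the day 75 and day 365 windows". It also requires that "7 consecutive days of blood sugar and insulin readings are documented within +/- 7 days of the visit window", and the Synopsis has the same rule. Section 4.1.3.1 words the diary criterion differently: at least 7 fasting capillary readings in seven days and, for the two-hour post-prandial limit, "based on measuring capillary glucose levels a minimum of 21 times in a seven day period". Only Section 4.1.3.1 has the 21-reading minimum; the other two places use the 90-minute meal-test glucose for that criterion.

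**LI** (secondary endpoint at the same times). Section 9.1.1.3 states: "The LI requires 4 or more daily capillary BG measurements over a 4 week period". LI is defined as a sum over consecutive readings 1 to 12 hours apart, expressed per week.

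**Missing data.** Section 10.2.2 imputes failure for an unevaluated dichotomous endpoint, unless an evaluation exists later than 75 days after transplant and before another infusion.

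**The concern.** The subjects excused from daily recording are the only ones who can qualify as full-function successes. A subject who follows Section 7.6 to the letter and is truly insulin-independent can lack the documentation that the endpoint demands, and Section 10.2.2 may then count that subject as a failure. The same subject's LI falls below its stated data minimum.

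Because insulin-free status arises after randomisation and reflects outcome, the missing data would concentrate in whichever arm does better. The label also travels. The Study Definitions Page treats anyone without full function as insulin-dependent, Section 10.2.2 plans models of full function over time and of time to insulin dependence, and Section 7.4.2 lists lack of full function among the conditions for considering a third infusion.

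Readings that were never taken cannot be restored by an analysis plan, so the conflict has to be settled in the protocol.

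**Working it through.** **1. Reproduce the plan's minima.** A recording day in Section 7.6 has 3 pre-meal, 3 post-meal and 1 evening reading, so 7 in all, of which 1 is fasting and 3 are post-prandial. Over seven days: 7 × 1 = 7 fasting and 7 × 3 = 21 post-prandial. These are exactly the minima in Section 4.1.3.1, so that definition presupposes the full schedule on every day.

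**2. Apply the allowance.** I read the seven diary days as belonging to the insulin-free week.

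| Quantity in 7 days | Required, or full schedule | At two days a week |
|---|---|---|
| Fasting readings | 7 | 2 × 1 = 2 |
| Post-prandial readings (Section 4.1.3.1 only) | 21 | 2 × 3 = 6 |
| All readings | 7 × 7 = 49 | 2 × 7 = 14 |
| Consecutive documented days | 7 | not attainable |

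The best case puts both days at the end of one week and both at the start of the next. A seven-day run then holds 4 recorded days, giving 4 fasting and 12 post-prandial readings, still short of both minima.

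**3. Effect on full graft function.** Suppose a proportion *u* of true successes in each arm use the allowance in the window and have no qualifying later evaluation. Under the imputation rule an arm's observed rate is p(1 − u), and the difference is (p₁ − p₂)(1 − u). The protocol gives no *u*, so the range runs from no loss (u = 0) to complete loss (u = 1).

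If sites instead scored whatever readings exist, the error would reverse: the criterion is breached only by more than three fasting values above 140 mg/dL, which cannot happen with two readings.

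**4. Effect on LI.** Read strictly, the daily minimum is unmet on five days of every seven and LI is not computable. If someone nevertheless sums the available pairs without rescaling, count the pairs 1 to 12 hours apart in 28 days. The reading hours are assumed: 7, 9, 12, 14, 18, 20 and 22, or 7, 12, 18 and 22 for four points.

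- Seven points daily: 28 × 6 within-day + 27 overnight = 195 pairs.
- Seven points, two days a week: 8 × 6 = 48 if the days are separate, 48 + 4 = 52 if adjacent. Ratios: 48/195 = 25%, 52/195 = 27%.
- Four points daily: 28 × 3 + 27 = 111 pairs. Two days a week: 24 or 28. Ratios: 24/111 = 22%, 28/111 = 25%.

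A simulation of autocorrelated hourly glucose (SD 1.0, 1.5 and 3.0 mmol/L; correlation time 2 and 4 hours; seven points) gave 26–28% of the full-diary LI. The overall range is therefore 22–28%. Rescaling by 7/2 restored 92–94% when the two days were not adjacent.

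**5. How much of each LI window is insulin-free.** Section 5.11 describes 2 days of IV insulin, a further 4 to 8 weeks of SC insulin, and reductions of at most 20% at 3-day intervals. Assume tapering starts when the SC period ends, on day 2 + 28 = 30 or day 2 + 56 = 58. Five steps span 4 × 3 = 12 days, so insulin stops at about day 42 or day 70. For the 28 days ending at Day 75, all 28 or about 75 − 70 = 5 are insulin-free. At Day 365 the whole window is affected for a subject still insulin-free.

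**The case against.** The strongest reply is that the allowance is a permission. A site can satisfy every section by having subjects record daily near visits, and the specific endpoint rules could be read as overriding a general floor. Around Day 75 the seven days may fall anywhere from day 63 to day 87. Appendix 1 also provides for glucometer downloads and, in note 5, a diary log at each visit.

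This stands in part: harm arises only where the allowance is actually used in a window. But the protocol states no precedence, tells sites twice that two days suffice, and sets no number of days for the diary log. A download holds only readings that were taken.

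A reader might infer four stronger claims that the document does not support:

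- *Every such success becomes a failure.* Section 10.2.2 accepts a later evaluation before another infusion. Since the allowance runs to month 12, that rescue still needs a later visit with enough readings.
- *LI is necessarily deflated.* With its minimum unmet, LI is missing. The low value appears only in an unscaled sum, and at Day 75 possibly for only part of the window.
- *HYPO breaches a daily requirement.* Section 9.1.1.4 asks for a four-week record and a 12-month recall, with no daily frequency. Events may be undercounted; no stated minimum is broken.
- *The treatment difference shrinks by a known amount.* Any figure depends on an uptake rate that the protocol does not give.

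MAGE can be met within the allowance if the two recording days are adjacent. The primary endpoint, 90-minute C-peptide at Day 75, does not use the diary.

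**Conclusion.** The contradiction is real and should be fixed, though it concerns secondary endpoints only. A compliant insulin-free subject who uses the allowance in a window cannot supply seven consecutive documented days, and gives about 2 of 7 fasting readings (and 6 of the 21 post-prandial readings asked for in Section 4.1.3.1 alone). Full graft function is then not evaluable and is imputed as failure, unless a later evaluation precedes any further infusion.

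LI is not computable. If it is summed unscaled anyway, it is about 22–28% of its full-diary value in a fully insulin-free window, under the assumed reading hours and glucose model. The Day 75 share further assumes that tapering starts at the end of the SC insulin period. The net effect on the arm comparison cannot be sized from the protocol.

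**What to change.** In Sections 7.6 and 9.1, state that the two-day allowance is suspended, whatever the subject's insulin status, for the data windows of the Day 75, Month 12 and Year 1 assessments:

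- the four-week period used for LI and HYPO, with at least four readings daily; and
- the seven consecutive days within ±7 days of the visit window, on the full seven-point schedule.

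At the same time, reconcile Sections 7.6 and 9.1 with the Study Definitions Page, the Synopsis, Section 4.1.3.1 and Section 9.1.1.3, so that one diary requirement for full graft function applies throughout.

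The change is one sentence in two places, plus the reconciliation, and affects data collection only. The cost falls on insulin-free subjects. If the seven days lie inside the four weeks, the minimum is 7 × 7 + 21 × 4 = 133 readings, against 8 × 7 = 56 under the allowance: 77 extra fingersticks per assessment. Outside these windows the allowance can stay.

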## 7.7 Visit Windows

VISIT NO.	VISIT	VISIT WINDOW
01	Screening/Enrollment	Date written informed consent is obtained until all information / results for evaluation of inclusion/exclusion criteria are complete.
02	Baseline Visit  / Waiting List	According to the pre-defined schedule detailed in the Schedule of Events (Appendix 1)
03	Transplant	Date of the islet transplantation
04-05	Day 1, Day 3	±0 days
06-09	Days 7, 14, 21, and 28	±3 days
10	Day 75	±5 days
11-12	Month 6, Month 12	± 14 days

#### Table 4. Visit Windows

If the patient requires additional islet transplantation(s), the previous follow-up period stops and a new visit period starts, beginning with the Baseline Visit.

## 7.8 Study Treatment Assignment Procedures

#### 7.8.1 Blinding and Randomization

This is an open-label study; therefore, no treatment codes are required for the assignment of study drug. Randomized treatment assignments will be developed by CIT-DCC statisticians and stored on the CIT-DCC server. The CIT-DCC will maintain a central web-based randomization system for the study. When a subject has been determined to be eligible, the site personnel will access the appropriate web page and complete the randomization procedures. At that time the system will verify that the patient is indeed eligible. If the patient is eligible, the site personnel and the islet laboratory (Rudbeck Laboratory, Uppsala, Sweden) will receive an email notification that the subject was successfully randomized, and will be provided the randomization assignment. The date and time of the randomization will be recorded in the database. Once a treatment assignment has been provided, the patient becomes a part of the intention-to-treat population. All randomized subjects will be included in the primary analysis for the study and will be assigned to the treatment to which they were randomized. A parallel and equivalent electronic telephone based system will provide back-up in the unlikely event that the web-based system is not available.

## 8. SAFETY MONITORING

Adverse events (AEs) that are classified as serious according to the definition set forth by the health authorities must be reported promptly to NIAID/NIDDK, Clinical Research Organization (CRO), Data Coordinating Center (DCC), health authorities, principal investigators, and the ethics committee (EC). This section defines the types of AEs and outlines the procedures for appropriately collecting, grading, recording, and reporting them. Information in this section complies with International Conference on Harmonization (*ICH*) *Guideline E2A: Clinical Safety Data Management: Definitions and Standards for Expedited Reporting* and *ICH E6: Guideline for Good Clinical Practice*, and applies the standards set forth in the current version of the Terminology Criteria for Adverse Events in Trials of Adult Pancreatic Islet Transplantation CIT-TCAE. This document, created by the Clinical Islet Transplantation (CIT) Consortium, modifies the National Cancer Institute (NCI), *Common Terminology Criteria for Adverse Events (CTCAE) version 3.0* (June 10, 2003), to ensure applicability in the setting of Islet Transplantation.

## 8.1 Definitions

### 8.1.1 Adverse Event (AE)

An AE is any occurrence or worsening of an undesirable or unintended sign, symptom (including an abnormal laboratory finding), or disease that is temporally associated with the use of a medicinal product whether considered related to the medicinal product or not.

